7.2.6 Sub-study blinding status

As this study has been proposed by collaborators at two PREPARE-ABC recruiting centres, it is possible that members of the sub-study team could be unblinded to treatment arm allocation of patients at their respective centres. They will remain blinded to the treatment arm allocation of patients at other centres. As this will only constitute a small overall proportion of patients for inclusion in the sub-study and a risk to the integrity of the sub-study analyses has not been identified, no further blinding procedures will be implemented for the sub-study teams.

Radiologists involved in carrying out CT scans as part of standard care as well as those involved in the analysis are independent of the study teams and thus will be blinded to intervention arm allocation. The CT analysis is automated and therefore further measurement bias is minimal. Any incidences of unblinding will be recorded on the eCRF.

7.2.7 Sub-study statistical methods

Statistical analysis will be performed using SPSS software (Version 24.0. SPSS Inc., Chicago, IL, USA).

Descriptive statistics will be used to analyse the baseline characteristics of the study population. For the primary outcome of muscle attenuation at 6-12 months post-procedure, the two groups (standard

care versus hospital-based and standard care versus home-based exercise interventions) will be compared using chi-squared test. Similar methods will be used to assess the change in muscle mass between each group, from baseline to their post-operative CT. Previous research (Martin et al) has suggested a standard deviation for this outcome of 9.4 HU. A difference in outcome between groups of 5 HU would be regarded as clinically important.

Dose Response Relationships

Using the self-reported physical activity data recorded in the patient exercise diaries, the sub-study team will correlate type and amount of exercise against changes in muscle mass. The muscle mass will be calculated as described above making particular note of mean muscle attenuation and L3 muscle area.

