7.2.1 Sub-study summary

Details specific to PREPARE-ABC are described in sections 1-7.1 of the PREPARE-ABC Protocol, the table below refers to details specific to the PREPARE-ABC sub-study only.

Table 4: Sub-study summary.

Source of Monetary or Material	Not applicable
Support	
Contact for Public Queries	[contact]
Contact for Scientific Queries on	[name] PhD
sub-study	[contact]
	Senior Clinical Lecturer and Honorary Consultant Colorectal
	Surgeon
	Academic Unit of Surgery
	[name]
	Glasgow Royal Infirmary
	[name]
	[name] MD
	[contact]
	Consultant Colorectal Surgeon and Honorary Senior Clinical
	Lecturer
	St Marks Hospital and Academic Institute
	[name]
	[name]
	[name]

Sub-study Scientific Title	Defining the relationship between hady composition
Sub-study Scientific Title	Defining the relationship between body composition, cardiorespiratory fitness and systemic inflammation in patients with operable colorectal cancer participating in the
	PREPARE-ABC trial.
Key Inclusion and Exclusion Criteria	In addition to the eligibility criteria for participation in the PREPARE-ABC study, the following sub-study eligibility criteria apply:
	 Have a pre-operative staging CT scan suitable for body composition (muscle and fat) analysis within the 6 months preceding enrolment in PREPARE-ABC Have height and weight recorded at baseline Have results available for full blood count and liver function tests (with or without CRP) taken within the 3 months preceding enrolment in the main trial
Sub-Study Type	This sub-study is performed in conjunction with PREPARE-
Sub Study Type	ABC analysing routine clinical and study-specific data.
Date of First Enrolment	Enrolment into PREPARE-ABC began in November 2016. This sub-study analysis uses routine and study-specific data collected from this point onwards.
Target Sample Size	285 participants (95 per group)
Primary Outcome(s) of sub-study	The following primary outcome will be assessed for standard
Trimary Successions (5) or sub-study	care versus hospital-based and standard care versus home- based exercise intervention groups:
	Outcome: Change in muscle mass attenuation on the pre- operative and first surveillance CT scans obtained as part of routine care. Metric: Assessed in Hounsfield units using slice-O-matic software.
Kara Casaradama Outasaasa af auh	The fellowing according when a will be accorded for

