7.2.3 Sub-study objectives

As in the main study, there will be three trial arms:

- Arm A Hospital based supervised exercise
- Arm B Home based supported exercise
- Arm C Standard care, treatment as usual

There are two primary research hypotheses:

- hospital-supervised exercise training in the pre- and post-operative period, in addition to standard care, leads to a change in muscle attenuation at 12 months versus standard care alone.
- home-supported exercise training in the pre- and post-operative period, in addition to standard care, leads to a change in muscle attenuation at 12 months versus standard care alone.

An exploratory hypothesis that hospital-supervised exercise training in the pre- and post-operative period, in addition to standard care, leads to a change in muscle attenuation at 12 months versus home-supported exercise will also be examined.

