7.2.4.3 Outcomes

7.2.4.3.1 Primary Outcomes

Outcome: Change in muscle mass

Change in muscle mass will be assessed using image analysis of the pre-operative and first surveillance CT scans obtained as part of routine care for standard care versus hospital-based and standard care versus home-based intervention groups.

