7.2.4.3.3 Sample size

The primary outcome is the change in mean muscle attenuation on CT at 6 months. For a comparison between two groups (standard care versus hospital-based and standard care versus home-based exercise interventions), a total of 95 participants per group (285 in total) will be required. This will have 90% power to detect a difference of 5 HU in mean muscle attenuation between any two treatment groups, assuming a standard deviation of 9.4 HU and a significance level of 5%, using a t-test. This will account for a drop-out rate of 20%.

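### The sub-study names a chi-squared test for a continuous primary outcome in Hounsfield units that was sized on a t-test, and it states that outcome and its time point in several ways

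*Protocol*

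**What the plan says.** All of this concerns the body-composition sub-study in section 7.2 of the protocol.

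- **Scale of the outcome.** The summary table in 7.2.1 gives the primary outcome as a change in attenuation between the pre-operative and first surveillance CT, "Assessed in Hounsfield units using slice-O-matic software".
- **Sample size.** Section 7.2.4.3.3 aims for 90% power to find a 5 HU gap in average attenuation when two arms are compared. The calculation is made "assuming a standard deviation of 9.4 HU and a significance level of 5%, using a t-test". With a 20% drop-out allowance this gives 95 per group, 285 in all.
- **Analysis.** Section 7.2.7 begins "For the primary outcome of muscle attenuation at 6-12 months post-procedure" and says that the arms ("home-based exercise interventions) will be compared using chi-squared test"). It extends the same approach to change in muscle mass, then restates the SD of 9.4 HU and the 5 HU difference regarded as clinically important.
- **Which variable and when.** The sample-size section says "The primary outcome is the change in mean muscle attenuation on CT at 6 months". The hypotheses in 7.2.3 say that exercise "leads to a change in muscle attenuation at 12 months versus standard care alone". Section 7.2.4.3.1 names a different quantity: "Change in muscle mass will be assessed using image analysis of the pre-operative and first surveillance CT scans".
- **Cut-offs.** The only muscle cut-offs are in 7.2.5. They apply to the skeletal muscle index in cm²/m², not to attenuation.

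**The concern.** A chi-squared test compares counts in categories. It makes no use of an SD or of a difference in means, which are the two quantities that sections 7.2.4.3.3 and 7.2.7 both rely on. As written, the primary analysis cannot be run until someone divides attenuation into categories, and the protocol supplies no division.

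Two things are at stake. An analyst who followed the sentence literally would have to choose a cut-point that was not pre-specified, would lose power, and would report a difference in proportions instead of the HU difference the sub-study calls important. An analyst who used a comparison of means would be doing the sensible thing but departing from the protocol.

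The varying definition makes this worse. Attenuation and amount of muscle are different measurements, and a scan at 6 months is not a scan at 12.

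**Working it through.** **1. Reproduce the stated sample size.** Inputs from 7.2.4.3.3: difference 5 HU, SD 9.4 HU, significance level 5%, power 90%, drop-out 20%, equal groups. Sidedness is not stated; two-sided is assumed.

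- Standardised difference: 5/9.4 = 0.532.
- Normal approximation: n = 2 × (1.960 + 1.282)² × (9.4/5)² = 74.3, so 75 per group.
- Noncentral t: 75 per group gives 89.9% power and 76 gives 90.3%, so 76 evaluable per group.
- Drop-out: 76/(1 − 0.20) = 95 per group, and 3 × 95 = 285.

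The plan's figure reproduces exactly as a two-sided t-test. A one-sided test would need 61 evaluable per group, which does not lead to 95. The number was therefore derived for a comparison of means.

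**2. What a chi-squared test would do with the same patients.** The protocol gives no cut-point, so this step is illustrative. It assumes attenuation is normal in each arm with SD 9.4 HU and a 5 HU shift. For a cut c, in SD units from the control mean, the proportions above the cut are:

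- control: 1 − Φ(c)
- exercise: 1 − Φ(c − 0.532)

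Power is for the Pearson chi-squared test without continuity correction, two-sided 5%, 76 per group. The first figure uses the normal approximation with pooled variance under the null. The second comes from exact enumeration of all possible tables.

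| Cut | Control | Exercise | Power, approximate | Power, exact |
|---|---|---|---|---|
| Midway between the means | 39.5% | 60.5% | 73.9% | 72.5% |
| Control median | 50.0% | 70.3% | 72.7% | 73.9% |
| Control 75th percentile | 25.0% | 44.3% | 71.1% | 71.6% |
| Control 25th percentile | 75.0% | 88.6% | 58.7% | 60.1% |
| Control 90th percentile | 10.0% | 22.7% | 56.2% | 57.7% |
| Control 10th percentile | 90.0% | 96.5% | 35.9% | 37.3% |

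Central cuts give about 72–74% and outer cuts about 36–72%, against 90.3% for the t-test. Even with no drop-out (95 evaluable per group) the best of these cuts reaches about 83%. To recover 90% at the midway cut would take about 118 evaluable, or 118/0.8 = 147.5, so 148 enrolled per group.

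**3. Set the definitions of the primary side by side.**

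| Section | Variable | Time |
|---|---|---|
| 7.2.1 | Change in muscle mass attenuation, HU | First surveillance CT |
| 7.2.3 | Change in muscle attenuation | 12 months |
| 7.2.4.3.1 | Change in muscle mass | First surveillance CT |
| 7.2.4.3.3 | Change in mean muscle attenuation | 6 months |
| 7.2.7 | Muscle attenuation | 6–12 months post-procedure |

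These do not describe one outcome. Naming the first surveillance CT does not settle the timing either, since 7.2.5 accepts surveillance scans at any point in the 12 months after surgery.

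**The case against.** **It is probably a slip in naming the test.** Section 7.2.7 repeats the 9.4 HU and 5 HU figures close to the chi-squared sentence, and 7.2.4.3.3 says t-test, so a comparison of means was very likely intended. That stands, and it lowers the severity. It does not remove the contradiction, because the protocol names two incompatible tests for one primary outcome.

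**A sub-study analysis plan is still to come.** Section 7.2.7.2 promises one, developed with the trial statisticians. It may already name a suitable test. But this is a method stated wrongly, not a detail left open: a plan that follows the protocol inherits the error, and one that corrects it departs from the protocol.

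**The power loss is hypothetical.** This stands. A reader might infer that the sub-study is underpowered, or that it cannot reach its stated 90%. The documents do not support that. They never propose dichotomising attenuation, and the 95 per group is correct for the analysis it was sized on. The lower figures show only what a literal use of the chi-squared test could cost.

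**Muscle mass is used loosely.** Sections 7.2.1 and 7.2.7 let the term cover attenuation as well as L3 area, so the difference in naming is softer than the difference in timing. Both still need one definition.

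**Conclusion.** Wrong as written. The test named in 7.2.7 does not fit a continuous outcome in HU and contradicts the t-test in 7.2.4.3.3. Extending similar methods to change in muscle mass carries the same fault to a second continuous variable. That conclusion rests on the protocol's text alone and needs no assumption.

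The sample size is sound, given a two-sided 5% test. The illustrated loss, from 90.3% to roughly 72–74% at best, depends on the assumptions in the working.

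The inconsistent primary variable and time point form a separate but real fault, and the same edit can cure it.

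Severity: should be fixed. A reader might take a wrong primary test as a defect in the trial itself, but it is confined to an ancillary study that uses trial and routine-care data. The main trial's outcomes, sample size and analyses do not depend on it.

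**What to change.** 1. In 7.2.7, replace the chi-squared test with a comparison of mean attenuation in HU. The preferred form is a linear model of follow-up attenuation on arm, baseline attenuation and site, reporting the between-arm difference in HU with its confidence interval. With baseline in the model, this also estimates the between-arm difference in change, so it agrees with the change wording elsewhere; the protocol should say so. Adjusting for site follows the main trial's rule for continuous outcomes in 5.10.4.6. A plain t-test would also remove the contradiction.
2. Use the same approach for change in muscle mass.
3. Do not put time from surgery to CT in the primary model. It arises after randomisation and could be affected by arm, for example if complications delay a scan. Keep it for a sensitivity analysis.
4. State one primary variable and one CT window, identically, in 7.2.1, 7.2.3, 7.2.4.3.1, 7.2.4.3.3 and 7.2.7, and carry them into the sub-study analysis plan.

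Cost: protocol and analysis-plan wording. N stays at 95 per group and no new data are needed.

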7.2.7.2 Sub-study statistical analysis plan

A sub-study statistical analysis plan (SAP) will be produced separately detailing all statistical aspects of this sub-study. The collaborating study teams will work to develop this plan with the trial statisticians and co-chief investigators. This SAP will be agreed by the PREPARE-ABC oversight committees as appropriate.

7.2.8 Sub-study publication policy

The results of the sub-study will be disseminated regardless of the direction of effect. Ownership of the data arising from this sub-study resides with the trial team and collaborating study teams. The publication(s) produced from this sub-study will be included in the publication policy of the main trial with the aim to publish in a peer-reviewed journal. The results of this sub-study will not be published prior to the publication of the results of the main trial.

8 Protocol Amendments

Document Name	Version No.	Effective Date	Reason for Change
Prepare-ABC	1.0		New protocol
Protocol			
Prepare-ABC	2.0	14.06.2016	Response to provisional opinion from Ethics
Protocol			committee
Prepare-ABC Protocol	3.0	23.09.2016	 Addition of trial identifying numbers in section 1.3 Update of questionnaire from BREQ-2 to BREQ-3 in sections 1.3, 5.5.2, 5.6, 5.6.1.2, 5.6.1.10 Trial diagram updated in section 2 to reflect when patients receiving preoperative chemotherapy will be recruited Stop/Go criteria in section 4.3.1 for the internal pilot stage updated to reflect strengthened criteria provided to HTA in response to full application. Confirmation on who can undertake the "Trial Physiotherapist" role for delivering the intervention at site Addition of grip-strength measurement at 30 days following surgery in sections 5.5.2 and 5.6 Change to section 5.4, 5.6.1.1 to when patients who are receiving pre-operative chemotherapy will be recruited to the study Removal of collection of expenses on patient questionnaire in 5.10.5 Addition of details of consent process for NHS staff providing information on standard care through telephone interviews with researcher in section 6.5.1 Addition of details of consent process for people attending appointments with patients (accompanying adult) Addition of analysis of data collected on standard care at each trust through telephone interviews with staff

			In addition to the above, minor administrative, typographical and formatting changes have been made throughout the protocol.
Prepare- ABC	4.0	16.05.2017	Update of Protocol Authorisation
Protocol			signatories
			Sections 1.42 -1.4.6 updated to following
			personnel changes and confirmation of
			committee members
			Clarification of who an act as local
			Principal Investigator (Section 5.1.2)
			 List of studies approved for co-
			enrolment updated (Section 5.3.1.4)
			Timeframe for pre-operative CPET
			amended to not more than 7 days pre-
			surgery (throughout Section 5.4 and
			5.6.1.5)
			Amendment of post-operative hospital
			based exercise sessions specifications to
			match pre-operative exercise sessions
			(Section 5.6.1.9)
			Clarification that home-supported
			patients should be exercising at 13-15 on
			the Borg RPE Scale in-keeping with the
			specifications for the hospital supervised
			exercise sessions (Sections 5.4.2, 5.6.1.4
			and 5.6.1.9)
			Clarification of post-operative exercise
			plans for hospital supervised patients
			(Sections 5.4.1 and 5.6.1.9) and home
			supported patients (Sections 5.4.2 and
			5.6.1.9)
			Addition of the option for patients to
			subscribe to a patient newsletter and

- update email service prior to discharge following surgery (Section 5.4.4)
- Addition to collect planned type of surgery (laparoscopic or data) (section 5.4)
- Addition to collect tumour histological stage data at 30 days post-surgery (section 5.4).
- Addition of information for sites regarding patients presenting with anaemia (Section 5.4.7)
- Participant Timeline table (Section 5.6)
 updated to allow flexibility around 30
 Day post-surgery and 6 and 12 Month
 follow up visits.
- Addition of SAE reporting method for sites (Section 5.11.3.7.1)
- Clarification of safety and per protocol definitions for patients randomised to all three treatment arms (Section 5.10.4.5)
- Removal of Section 6.2 (from v3.0, 23/09/2016) as Competent Authority Approvals are not applicable to this study
- Addition to permit the audio recording of intervention counselling sessions observed as part of the Process Evaluation and description of transcription analysis arrangements for the recordings (Section 7.1)
- Follow-up period following patient interviews carried out as part of the Process Evaluation reduced to 3 Months (Section 7.1)

			Addition of recommendations for
			optimising questioning and advice giving
			within counselling sessions as a
			component of the qualitative data
			analysis (Section 7.1)
			Section 7.1 new reference added
			In addition to the above, minor administrative,
			typographical and formatting changes have been
			made throughout the protocol.
Prepare- ABC	5.0	01.03.2018	Section 1.3 – Addition of Ireland to
Protocol			recruiting countries
			Section 1.4 – Protocol contributors, trial
			management group and trial team lists
			updated.
			Section 5.3.1.1 – Additional clarification
			on approaching patients with metastasis
			 Section 5.3.1.2 – Clarification on
			intention of exclusion criteria to exclude
			patients for whom exercise in unsafe.
			Section 5.3.1.4 - Updated list of
			studies/projects where co-enrolment
			with PREPARE-ABC is and is not
			permitted
			 Section 5.4 – Clarification that patients
			found to have benign tumours post-
			operatively can remain in the study as
			per protocol.
			Section 5.6.1.4 – section on CPET
			guidance added.
			Section 5.6.1.5 - Clarification that
			patients should be encouraged to attend
			as many pre-operative supervised
			sessions as possible as opposed to a set
			minimum number of sessions.

- Section 5.6.1.6 Clarification that in the event where a patients surgery is delayed and the patient is randomised to an intervention arm, they should continue to exercise up until their surgery has taken place.
- Section 5.6.1.11 Addition of option for patients to consent to receive newsletters/trial updates during their participation.
- Section 5.9.2 Clarification on the blinding status of local study teams and independent assessors.
- Section 6.4.1 option for patients to express interest to be contacted for participation in Process Evaluation during consent process for main trial.
- Section 6.4.1 addition for patients
 already enrolled in the study who were
 not approached for participation in the
 PE, at the time of consent to the main
 trial, to express verbal consent to the
 local study team prior to sending
 relevant consent form for completion via
 post.
- Section 7.1 addition to allow site study staff to audio record counselling sessions if UEA research associate is unable to attend session and patient has provided written consent.
- Section 7.1 Clarification that the Process Evaluation will be conducted at UK sites only.

			In addition to the above, minor administrative,
			typographical and formatting changes have been
			made throughout the protocol.
PREPARE-ABC	6.0	05/09/2019	• Sections 1.1, 5.10.1 and 7.2.5 - Inclusion
Protocol			of General Data Protection Regulation
			(2018) adherence following
			implementation of legislation
			Sections 1- 7 - Amendments to ensure
			study specific terminology is consistent
			Section 1.4 - Update of study personnel
			and their affiliated institutions including
			removal of individuals no longer
			associated with the trial
			• Sections 2, 4 – 5 - Update of pre-
			operative exercise period to 2-4 weeks
			(including on trial diagram)
			• Sections 4.1.2, 5.4.3, 5.6.1.5, 5.6.1.10 -
			Confirmation that exercise advice
			offered as part of standard care will
			remain for all patients recruited into the
			trial and no advice regarding exercise
			(outside of this) will be offered to
			patients randomised to the
			control/treatment as usual arm
			Section 5.1.2 - Clarification that a CPET
			lead only need be named for sites where
			available
			• Sections 5.3.1.1 and 5.3.1.4 -
			Clarification regarding the timeframe for
			co-enrolment assessments
			Section 5.3.1.4 - Clarification that co-
			enrolment assessments are still required
			where patients remain in follow-up

- and/or have discontinued trial treatment in the opposite trial
- Section 5.3.1.4 Update to list of studies where co-enrolment has and/or has not been agreed
- Section 5.3.1.3 Confirmation of and details of remote exercise intervention training
- Section 5.4.1 and 5.6.1.5 Clarification that up to 3 sessions per week are offered in the pre-operative phase for hospital supervised patients
- Section 5.4.1.1 Addition of modified recruitment pathway for patients expressing concerns around randomisation to the hospital-supervised exercise arm
- Section 5.4.4 Clarification of timing of consent for and arrangement regarding the patient newsletter (removed duplicated information from section 5.6.1.11)
- Section 5.6, 5.6.1.11 Increased
 flexibility for the scheduling of the 6 and
 12M follow-up visits to +/-6 weeks
- Section 5.6.1.4 Clarification of the preferred format for CPET results
- Section 5.6.1.9 Addition to text that grip strength should be measured at the 30days post-surgery visit
- Section 5.6.1.8 and 5.6.1.9 Clarification of timelines for recording post-operative complications

- Section 5.8.1 Update of the trial recruitment period
- Section 5.8.1.1 Confirmation that research associates can approach patients who have consented to or are interested in the process evaluation assessments
- Section 5.10.4.1 Confirmation that an interim statistical analysis plan will be produced for all planned interim analyses
- Section 5.11.3.6.2 Confirmation of expectedness assessments for serious adverse events
- Section 5.11.3.6.2 Clarification of recording requirements for serious but unrelated adverse events
- Section 6.2 Confirmation that site specific information forms will be completed for sites in devolved nations
- Section 6.5 Confirmation that only patient age in years will be recorded as opposed to month and year as previously listed
- Section 6.10 Confirmation that trial data will not be shared with collaborators without TMG and TSC approval on an individual basis
- Section 7.2 7.2.8 Addition of the PREPARE-ABC sub-study: defining the relationship between body composition, cardiorespiratory fitness, systemic inflammatory response and postoperative outcomes in patients with

	T	1	1
			operable colorectal cancer participating
			in the PREPARE-ABC trial
			Section 9 – References updated as in text
			citations require.
			In addition to the above, minor administrative,
			typographical and formatting changes have been
			made throughout the protocol.
PREPARE-ABC	7.0	11/02/2020	• Sections 2, 4 – 5 - Update of pre-
Protocol			operative exercise period to 3-4 weeks
			(including trial diagram)
			Section 5.3.1.4 - Update to list of studies
			where co-enrolment has and/or has not
			been agreed
			• Section 5.4.1 and 5.6.1.5 – Removal of
			clarification that up to 3 sessions per
			week are offered in the pre-operative
			phase for hospital supervised patients
			Section 5.4.1.1 – Removal of the addition
			of modified recruitment pathway for
			patients expressing concerns around
			randomisation to the hospital-supervised
			exercise arm
			In addition to the above, minor
			administrative, typographical and
			formatting changes have been made
			throughout the protocol.
PREPARE-ABC	8.0	23/06/2020	Section 5.4.1 – added a note referencing
Protocol		10, 50, 2020	the updates regarding the temporary
			suspension of Arm A due to COVID-19 in
			section 5.12.
			• Sections 5.6.1.11 and 5.10.1 adding
			clarification for postal or online
			completion of the questionnaires as

face-to-face visits will be reduced due to
COVID-19
Addition of Section 5.12 to outline the
impact and adaptations as a result of
COVID-19 including the temporary
suspension of Arm A (hospital supervised
exercise)
 In addition to the above, minor
administrative, typographical and
formatting changes have been made
throughout the protocol.

9 References

ACPGBI (2015) http://www.acpgbi.org.uk/surgeon-outcomes/

Artinyan, A., S. T. Orcutt, D. A. Anaya, P. Richardson, G. J. Chen and D. H. Berger (2015). "Infectious postoperative complications decrease long-term survival in patients undergoing curative surgery for colorectal cancer: a study of 12,075 patients." Ann Surg 261(3): 497-505.

